1. SYNOPSIS

Clinical Study Title:	A multi-center, open-label, in-use study to assess efficacy and tolerability of topical skincare products on psoriasis patients
Clinical Trial Number:	GLI.04.US.SL.035
Clinical Study Phase:	Phase 4
Indication:	The study products will be applied topically.
Study population:	Adult subjects having mild-to-severe plaque psoriasis, with active target lesion plaques, and currently on or starting a prescription treatment for plaque psoriasis
Country(ies) Involved and Planned Number of Study Centers:	USA Sites: 2 sites at 3 study centers
Number of Subjects:	40-50 subjects to complete, with 20-25 subjects to complete per study site.
Clinical Study Design:	
This is a multi-center, open-label, in-use study.
 
Subjects will report to the site at Baseline (day 0) visit, will be given an informed consent form, HIPAA form, photography release form, and medical history form to complete.
 
Subjects will be screened on the basis of the selection criteria for study qualification. Eligible subjects will be assessed at Baseline visit and instructed to start applying the skincare products to the assigned side of the body based on the pre-determined randomization.
 
Subjects to return to the site at Week 2 (\pm 3 days), Week 4 (\pm 5 days), and Week 8 (\pm 5 days) for follow-ups.

Primary Objective	To assess efficacy and tolerability of skincare products when used in conjunction with prescription treatment for plaque psoriasis via investigator and subject assessments at follow-up visits compared to Baseline.
Secondary Objective(s)	To evaluate subject's life quality using Quality of Life (QoL) questionnaire at the end of the study compared to Baseline.

	To characterize the study treatment satisfaction using self-assessment questionnaires at each follow-up visits.
Exploratory Objective:	To assess change in skin parameters via imaging analysis at follow-up visits compared to Baseline.
Clinical Study Duration:	The planned duration of recruitment and study visit (from FSI to LSO) is approximately 5 months.
Duration of Subject Participation:	Clinical study participation for subjects is 8 weeks.
Inclusion criteria:	
The subjects must meet all the following criteria to be eligible for the study:
 
 1. Adult subjects aged 18 years and above 2. Females or males 3. Any Fitzpatrick skin types I-VI, with effort to include n = 2 for each category 4. Any races, with effort to include minimum 10% minority (n = 4) such as American Indian or Alaska Native, Eastern/Southeastern Asian, South Asians, Black or African American, Native Hawaiian or Other Pacific Islander. 5. Any ethnicities, with effort to include minimum 10% (n = 4) of Hispanic, Latino, or Spanish origin 6. Having active target lesion plaques, with minimum area of 2 cm x 2 cm 7. Having mild-to-severe plaque psoriasis with at least 3% Body Surface Area (BSA) and cumulative Target Lesion Severity Score (TLSS) ≥ 6. 8. Currently on or starting a plaque psoriasis prescription treatment such as biologics, oral or topical therapy for psoriasis, or UV therapy. 9. Subject in general good health 10. Subject willing to stop using current topical skincare products during the duration of the study. 11. Subject willing to replace current skincare products with study products for the duration of the study. 12. For female subjects of childbearing potential, she must not be pregnant, breastfeeding or planning pregnancy during the course of the study. Subjects must be willing to take a urine pregnancy test (UPT) at Baseline visit. 
 ▪ Females of non-childbearing potential, e.g., post-menopausal (absence of menstrual bleeding for 1 year without any other

	
medical reason), hysterectomy, or bilateral ovariectomy, are not required to have a UPT.
 
13. Ability of giving consent for participation in the study
 
14. Willing to sign a photography release, with minimum 80% of total study panel
 
15. Agreement to adhere to the procedures and requirements of the study and to report to the site on the day(s) and at the time(s) scheduled for the assessments

Exclusion criteria:	
The presence of any of the following exclusion criteria excluded a subject from enrollment in the study:
 
 1. Pregnant, breastfeeding, or planning pregnancy during the course of the study. 2. Subjects with any known allergies or hypersensitivity to any cosmetics, personal care products, and/or fragrances. 3. History of cancer within the past 5 years 4. History or presence of any skin condition/disease, besides plaque psoriasis, that might interfere with the diagnosis or evaluation of study parameters at the discretion of the investigator. 5. Planning on having surgeries and/or invasive medical procedures during the course of the study 6. Treatment with chemotherapy, immunosuppressive agents, prescription corticosteroids for psoriasis, immunomodulatory therapy (e.g., monoclonal antibodies or antiviral treatment for human immunodeficiency virus or hepatitis C) 7. History or presence of any medical condition that, in the opinion of the Investigator, would make the subject unsuitable for inclusion (e.g., a chronic, relapsing, or hereditary disease that may interfere the outcome of the study). 8. Other condition preventing the subject from entering the study in the Investigator's opinion, (e.g., subjects failing baseline assessments, subjects not likely to avoid other treatments in the treated areas, subjects anticipated to be unavailable or incapable of understanding the study assessments or having unrealistic expectations of the treatment result). 9. Study site personnel, close relatives of the study site personnel (e.g., parents, children, siblings, or spouse), or employees and close relatives of employees at the Sponsor company. 10. Participation in any interventional clinical study within 30 days of screening or planning to participate in another interventional clinical research study while enrolled in this trial.

Investigational Products:	Cetaphil® Moisturizing Cream Cetaphil® Gentle Skin Cleanser Cetaphil® Daily Facial Moisturizer SPF 35 (supporting product)
Treatment Area / Treatment Regimen / Mode of Administration	Step 1: clean the skin with the study cleanser once daily. Step 2: with clean dry hands, apply the study moisturizing cream to the lesion areas. The study moisturizing cream will be applied at least twice daily, in tandem with prescription psoriasis treatment, following the provided instructions. Subjects may apply the test product more frequently as needed.
Effectiveness Assessments:	BSA, TLSS, and PSA grading by investigator. Standardized photography of target lesions using digital camera. Macroscopic camera with imaging analysis, and capacitance imaging system (Site 2 only). Treatment satisfaction using QoL and self-assessment questionnaire.
Safety Assessments:	Tolerability assessment by investigator and subject. Adverse Events will be obtained from signs and symptoms reported by the subject or detected during study visit.
Statistical Methods:	In general effectiveness, safety and baseline characteristics variables will be presented using descriptive statistics, and graphs as appropriate. Continuous endpoints will be summarized using descriptive statistics, e.g., mean, median, standard deviation, minimum and maximum values. Categorical endpoints will be presented in frequency tables with number and percentage of observations for each level.

2. LIST OF ABBREVIATIONS AND DEFINITION OF TERMS

AE	Adverse Event
BSA	Body Surface Area
Childbearing Potential	A female (including pre-menopausal subjects) capable of becoming pregnant; this includes women on oral, injectable, or mechanical contraception or women whose male partners have been vasectomized or are utilizing mechanical contraceptive devices
CTA	Clinical trial agreement
CTN	Clinical trial number
CV	Curriculum vitae
EC	Ethics Committees
EOS	End of Study
FSI	First subject in, i.e., first subject who signs the informed consent form
FST	Fitzpatrick Skin Type
GCP	Good clinical practice
GDPR	General Data Protection Regulation
ICF	Informed Consent Form
ICH	International Conference on Harmonization
IFU	Instructions for use
Investigator	The Principal Investigator (PI) or other qualified person, i.e. sub-Investigator, designated and supervised by the PI at a study site to perform critical study-related procedures or to make important study-related decisions as specified on the signature and delegation log
Investigator file	Essential documents relating to a clinical study as defined in applicable GCP guidance document and maintained by the Investigator.
ISO	International Organization for Standardization
ITT	Intention-to-treat
LSO	Last subject out
MedDRA	Medical Dictionary for Regulatory Activities
NSAID	Non-steroidal anti-inflammatory drugs
PGA	Physician Global Assessment
PI	Principal Investigator; qualified person responsible for conducting the study at a study site

Protocol GLI.04.US.SL.035

CONFIDENTIAL

SAE	Serious Adverse Event
TLSS	Target Lesion Severity Score
Study products	The products used for treatment in under study
Study site	Institution or site where the study is carried out
Tx	Treatment
UPT	Urine pregnancy test
VAS	Visual Analogue Scale
WHO	World Health Organization

3. BACKGROUND AND RATIONALE

Psoriasis is a chronic inflammatory skin condition that affects 2% of the population worldwide, and is characterized by the formation of distinct, scaly, erythematous plaques.^{1, 2} These plaques can be painful, pruritic, and disfiguring. Psoriasis can substantially diminish quality of life and negatively affect patient's well-being.² In mild to moderate disease, first-line treatment typically involves topical therapies, such as corticosteroids, vitamin D3 analogues and combination products. Biologic agents have emerged as highly potent treatment options for moderate to severe psoriasis; however, because complete clearance is not always achieved by a biologic agent, most patients who receive biologic therapies continue to use adjunctive topical therapies³.

Skincare products in the treatment of psoriasis have historically been thought to provide only symptomatic relief, but new evidence suggests moisturizers may confer therapeutic benefit by supporting epidermal barrier repair. Patients with psoriasis are advised to moisturize using lipid-replenishing ointments or creams to relieve itching and prevent skin dryness, and as such, frequent application of moisturizers has been standard in the management of psoriasis⁴. Other researchers have noted that moisturizers can confer therapeutic effects in psoriasis⁵. One study involving Cetaphil Moisturizing Cream found that use of moisturizer alone prevented further damage to skin barrier and increased skin hydration⁶. This study is to assess the efficacy of Cetaphil skincare products when used in conjunction with prescription treatment for plaque psoriasis.

4. STUDY OBJECTIVES AND CLINICAL HYPOTHESIS

4.1 Study Objectives

The primary objective of this study is:

- To assess efficacy and tolerability of skincare products when used in conjunction with prescription treatment for plaque psoriasis via investigator and subject assessments at follow-up visits compared to Baseline.

The secondary objectives of this study are:

- To evaluate subject's life quality using Quality of Life (QoL) questionnaire at the end of the study compared to Baseline.
- To characterize the study treatment satisfaction using self-assessment questionnaires at each follow-up visits.

The exploratory objective of this study is:

- To assess change in skin parameters via imaging analysis at follow-up visits compared to Baseline.

4.2 Clinical Hypothesis

The study skincare products will produce a statistically significant decrease in psoriasis clinical grading scores over the course of 8 weeks of use when compared with baseline scores. Additionally, the study products will be well tolerated by subjects, with no statistically significant increases in scores for tolerability parameters at any study time point when compared to baseline

Protocol GLI.04.US.SL.035

CONFIDENTIAL

scores. Furthermore, the study products will be well perceived by subjects according to analyses of QoL assessment, with a statistically significant improvement in subject response values when compared with baseline, and self-assessment questionnaire, with a statistically significant proportion of favorable responses compared to unfavorable responses.

For the explorable endpoint, the study products will produce a statistically significant improvement in efficacy via imaging analysis values over the course of the study when compare with baseline.

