6.2 Study Population Characteristics

Adult subjects having mild-to-severe plaque psoriasis, with active target lesion plaques, and currently on or starting new prescription treatment for plaque psoriasis.

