6.3 Inclusion Criteria

The subjects must meet all the following criteria to be eligible for the study:

1. Adult subjects aged 18 years and above
2. Females or males
3. Any Fitzpatrick skin types I-VI, with effort to include $n = 2$ for each category
4. Any races, with effort to include minimum 10% minority ($n = 4$) such as American Indian or Alaska Native, Eastern/Southeastern Asian, South Asians, Black or African American, Native Hawaiian or Other Pacific Islander.
5. Any ethnicities, with effort to include minimum 10% ($n = 4$) of Hispanic, Latino, or Spanish origin
6. Having active target lesion plaques, with minimum area of 2 cm x 2 cm
7. Having mild-to-severe plaque psoriasis with at least 3% Body Surface Area (BSA) and cumulative Target Lesion Severity Score (TLSS) ≥ 6 .
8. Currently on or starting a plaque psoriasis prescription treatment such as biologics, oral or topical therapy for psoriasis, or UV therapy.
9. Subject in general good health
10. Subject willing to stop using current topical skincare products during the duration of the study.
11. Subject willing to replace current skincare products with study products for the duration of the study.
12. For female subjects of childbearing potential, she must not be pregnant, breastfeeding or planning pregnancy during the course of the study. Subjects must be willing to take a urine pregnancy test (UPT) at Baseline visit.
 - Females of non-childbearing potential, e.g., post-menopausal (absence of menstrual bleeding for 1 year without any other medical reason), hysterectomy, or bilateral ovariectomy, are not required to have a UPT.

Protocol Version 02: 29 January 2024

This document contains confidential, proprietary information.

Protocol GLI.04.US.SL.035

CONFIDENTIAL

13. Ability of giving consent for participation in the study
14. Willing to sign a photography release, with minimum 80% of total study panel
15. Agreement to adhere to the procedures and requirements of the study and to report to the site on the day(s) and at the time(s) scheduled for the assessments.

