6.5 Concomitant Therapies

All treatments and therapies used 30 days prior to enrollment and all treatments or therapies used during the course of the study must be recorded in the Case Report Form (CRF) or electronic Case Report Form (eCRF).

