6.5.1. Authorized Therapies

Prescription treatments for plaque psoriasis, including biologics, oral or topical therapy for psoriasis, and UV therapy, are required for this study.

Protocol Version 02: 29 January 2024

This document contains confidential, proprietary information.

Protocol GLI.04.US.SL.035

CONFIDENTIAL

Unless listed under the exclusion criteria (see Section 6.4) or in Prohibited Therapies (see Section 6.5.2), other therapies to treat ongoing conditions are authorized.

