12.4 Statistical Analysis Plan

Mean of the change from Baseline will be estimated at applicable post-Baseline timepoint. The null hypothesis, that the mean change from Baseline is zero, will be tested using methods described in

Table 5.

The following will be calculated and reported for each parameter at applicable post-Baseline timepoint(s):

$$\text{Percent mean change from baseline} = \frac{(\text{visit mean score} - \text{baseline mean score})}{\text{baseline mean score}} \times 100$$

$$\text{Percent of subjects improved/worsened} = \frac{(\text{number of subjects improved/worsened from baseline})}{\text{total number of subjects}} \times 100$$

Protocol Version 02: 29 January 2024

This document contains confidential, proprietary information.

Protocol GLI.04.US.SL.035

CONFIDENTIAL

Table 5. Statistical Analysis Plan

Evaluation	Change from Baseline	Notes/Interpretation
Clinical Grading 
 BSA TLSS PGA 	One-sample t-test; If normality fails, a Wilcoxon signed-rank test will be used.	A decrease in scores indicates an improvement.
Tolerability Grading 
 Dryness Burning/Stinging Itching 	One-sample t-test; If normality fails, a Wilcoxon signed-rank test will be used.	A decrease in scores or lack of significant increase indicates tolerability/safety of the treatment products.
Macroscopic Imaging 
 Skin smoothness Skin roughness 	One-sample t-test; If normality fails, a Wilcoxon signed-rank test will be used.	A decrease in values indicates an improvement in skin smoothness. An increase in values indicates an improvement in roughness.
Capacitance Imaging 
 Homogeneity 	One-sample t-test; If normality fails, a Wilcoxon signed-rank test will be used.	An increase in values indicates a homogeneous moisture distribution.
QoL Questionnaire	Wilcoxon signed-rank test	A decrease in response values indicates an improvement.
Self-Assessment Questionnaire	N/A	Percentage of favorable and unfavorable responses will be provided for each question.

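### Section 4.2 credits the skincare products with any fall in BSA, TLSS and PGA, but the pooled test against Baseline cannot separate their effect from that of a prescription that may be only just starting

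*Combined protocol and SAP*

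**What the plan says.** All references are to the combined protocol and SAP.

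- **Hypothesis (4.2).** "The study skincare products will produce a statistically significant decrease in psoriasis clinical grading scores over the course of 8 weeks of use", compared with baseline scores. The products are the subject of the sentence, so the claim is causal.
- **Primary objective (4.1).** "To assess efficacy and tolerability of skincare products when used in conjunction with prescription treatment for plaque psoriasis". This is softer, but what is assessed is still the efficacy of the skincare products.
- **Who enters.** Inclusion 8 in section 6.3 reads "Currently on or starting a plaque psoriasis prescription treatment such as biologics, oral or topical therapy for psoriasis, or UV therapy". Section 6.2 describes subjects "currently on or starting new prescription treatment for plaque psoriasis". No minimum time on the prescription and no stable regimen is required.
- **Background treatment (6.5.1).** "Prescription treatments for plaque psoriasis, including biologics, oral or topical therapy for psoriasis, and UV therapy, are required for this study".
- **Test (12.4, Table 5).** For BSA, TLSS and PGA: "One-sample t-test; If normality fails, a Wilcoxon signed-rank test will be used". The null hypothesis is zero mean change from Baseline, the level is two-sided 5% (12.1), and the primary set is ITT (12.2). Prescription status is not a stratum, covariate, subgroup or sensitivity analysis.
- **Data at hand (6.5).** "All treatments and therapies used 30 days prior to enrollment", and those used during the study, go into the case report form. No analysis uses them.

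**The concern.** In a subject who begins an effective prescription around the Baseline visit, the prescription alone can be expected to lower the scores over 8 weeks. The protocol does not regard this effect as negligible. Its background section says "Biologic agents have emerged as highly potent treatment options for moderate to severe psoriasis", and biologics are among the prescriptions that inclusion 8 names. A one-sample test of pooled change responds to any cause of improvement, so it can reject its null when the moisturizer and cleanser do nothing.

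What is at stake is the meaning of the primary conclusion. A significant p value would be read through section 4.2 as evidence that the products work, when the analysis supports only the statement that subjects improved on the combination.

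**Working it through.** **Is there a control that would rescue attribution?** Section 5 says products go on an assigned side of the body according to a randomization, and section 9.1.1 includes a randomization step. Section 8.3.1, however, has the moisturizer applied to the lesions and the whole body, and Table 5 contains no comparison between sides. As written there is no untreated side and no between-side test, hence no usable control.

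**Inputs from the documents.** 40 to 50 completers (6.1); one-sample t-test against zero, two-sided 5%. The plan gives no power, SD or effect size, so it has no figure to reproduce.

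**Assumed inputs.** Product effect zero; share of starters f; mean prescription effect in starters d, in TLSS points; no mean change in the others; within-group SD of change s.

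**Formulas.**
- Pooled mean change = −f × d, all of it from the prescription.
- Pooled SD ≈ √(s² + f(1 − f)d²).
- The t statistic centres near √n × f × d / pooled SD in absolute size, against a critical value of 2.02 at n = 40.

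Worked case, n = 40, f = 0.25, d = 5, s = 3: mean fall 1.25; pooled SD √(9 + 0.1875 × 25) = √13.69 = 3.70; centre 6.32 × 1.25 / 3.70 = 2.14. That lies just above 2.02, so a little over half of such trials would show a significant decrease. Simulation of the t-test gives the exact behaviour:

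| Starters f | Prescription effect d | SD s | Chance of a significant decrease, n = 40 |
|---|---|---|---|
| 0 | – | 3 | 2.5% |
| 10% | 5 | 3 | 12% |
| 25% | 3 | 3 | 27% |
| 25% | 5 | 3 | 55% |
| 25% | 7 | 3 | 78% |
| 50% | 5 | 3 | 99% |
| 25% | 5 | 2 | 82% |
| 25% | 5 | 4 | 38% |
| 25% | 5 | 5 | 27% |

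At n = 50 the 55% case rises to about 64%: a larger sample makes it easier to detect the prescription effect. The Wilcoxon alternative behaves similarly. With d equal to 1 SD and n = 40, it gives 25% against 28% for the t-test at 25% starters, and 78% against 81% at 50%.

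**Would testing only subjects on an ongoing prescription settle it?** No. Entry requires BSA of at least 3% and TLSS of at least 6, which invites regression to the mean, and some of these subjects may still be improving on their prescription. An assumed drift of 1 TLSS point (SD 3) in all of them gives a significant decrease about 29% of the time at n = 20 and 54% at n = 40.

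**Would requiring an unchanged prescription through Week 8 help?** It selects on a post-baseline event. Suppose the worst 20% at Week 4 change prescription and are removed, with a Week 4 to Week 8 correlation r of 0.5 to 0.7. The mean of the remaining 80% of a normal distribution shifts by 0.28/0.80 = 0.35 SD at Week 4. At Week 8 the shift is 3 × 0.35 × r, or 0.5 to 0.7 TLSS points towards improvement, with no effect of anything.

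**Precision after a split.** 95% half-width = t × s/√n with s = 3: 2.093 × 3/√20 = 1.40 points at n = 20, and 2.023 × 3/√40 = 0.96 at n = 40.

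**The case against.** The strongest reply is that this is an in-use study of skincare alongside a prescription, that the primary objective says so, and that the bias cannot be sized from the documents. Part of that stands. The overclaim sits chiefly in 4.2, and the starter share, prescription effect and SD are all assumptions. But 4.2 and 12.4 set out hypothesis tests with p values, so calling the study descriptive does not answer the attribution problem.

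Four stronger readings are tempting and are not supported:

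- **A false positive is nearly certain.** That holds only with about half starters and a large prescription effect. At 10% starters the figure is 12%. The documents neither state nor cap the share.
- **Moving the primary test to established users cures the problem.** That test is still uncontrolled, and it would depart from ITT as the stated primary population.
- **Section 6.5 already holds all that is needed.** It requires therapies to be recorded but does not mention start dates.
- **DLQI, itching, dryness and imaging are inflated to the same degree.** They share the same uncontrolled comparison, but the documents give no basis for sizing a bias in them.

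Exclusion 6 also matters. It bars immunosuppressive agents, prescription corticosteroids for psoriasis and immunomodulatory therapy such as monoclonal antibodies, which conflicts with inclusion 8 and 6.5.1. How this is reconciled affects which starters can enrol and how strong their prescription effect could be. It does not remove the mixture of starting and ongoing users.

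**Conclusion.** The concern holds as a failure of attribution. The planned test cannot tell the products' effect from the prescription's, and section 4.2 claims the former. This follows from the text alone and needs no assumed figure.

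The size is conditional. With zero product effect, n = 40 and SD 3, the chance of a significant decrease runs from 12% to 99% over the scenarios shown. At 25% starters and a 5-point effect, it runs from 82% to 27% as the SD goes from 2 to 5. A reader might infer that the result is bound to be spurious, or that the products do not work; the documents support neither. The correction should be made before results are seen, because 12.4 allows a more appropriate analysis to be substituted and recorded only in a note to file or the study report.

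**What to change.** 1. **Reword 4.2 and the primary objective (synopsis and 4.1)** so that pooled results describe change from Baseline under prescription plus skincare, not an effect produced by the products. This is the essential part.
2. **In 12.4, keep the ITT set and pre-specify** that change in BSA, TLSS and PGA (estimate and 95% CI) is also reported separately for subjects on an ongoing prescription and subjects newly starting one. Classify by status at Baseline only, from the 6.5 records, and capture the prescription start date there. Any restriction to prescriptions unchanged through Week 8 should be at most a sensitivity analysis.
3. **State the limitation:** results in ongoing users remain uncontrolled and open to regression to the mean and residual prescription improvement.
4. **Reconcile the text:** exclusion 6 with inclusion 8 and 6.5.1; and the randomization and assigned-side wording with the whole-body use in 8.3.1.

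The cost is protocol and SAP wording plus one date field, with no new visits or procedures. The downsides are a more modest claim and wider subgroup intervals: a half-width of about 1.40 TLSS points at n = 20 against 0.96 at n = 40, if the SD is 3.
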